Period	A subdivision of the study timeline; divides stages into smaller functional segments such as screening, baseline, titration, washout, etc.
Personal data	Subject information collected by the Investigator that is transferred to Novartis for the purpose of the clinical trial. This data includes patient identifier information, study information and biological samples.
Randomization number	A unique treatment identification code assigned to each randomized patient, corresponding to a specific treatment arm assignment
Stage related to study timeline	A major subdivision of the study timeline; begins and ends with major study milestones such as enrollment, randomization, completion of treatment, etc.
Stage in cancer	The extent of a cancer in the body. Staging is usually based on the size of the tumor, whether lymph nodes contain cancer, and whether the cancer has spread from the original site to other parts of the body
Stop study participation	Point/time at which the patient came in for a final evaluation visit or when study treatment was discontinued whichever is later
Study treatment	Includes any drug or combination of drugs in any study arm administered to the patient (subject) as part of the required study procedures, including placebo and active drug run-ins. In specific examples, it is important to judge investigational treatment component relationship relative to a study treatment combination; study treatment in this case refers to the investigational and non-investigational treatments in combination.
Study treatment interruption	Includes any delay or withholding of study treatment for any reason as well as an interruption during an infusion of study treatment for any reason
Study treatment discontinuation	Point/time when patient permanently stops taking study treatment for any reason
Treatment group	A treatment group defines the dose and regimen or the combination, and may consist of 1 or more cohorts. Cohorts are not expanded, new cohorts are enrolled.

Variable	Identifier used in the data analysis; derived directly or indirectly from data collected using specified assessments at specified time points
Withdrawal of study consent	Withdrawal of consent from the study occurs only when a subject does not want to participate in the study any longer, and does not allow any further collection of personal data

Amendment 7 (27-Jan-2023)

Amendment rationale

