6.2.4 Definition of dose limiting toxicities in the safety-run in part (part 1)

A DLT is defined as (1) an adverse event or abnormal laboratory value assessed as unrelated to disease, disease progression, inter-current illness, or concomitant medications that occurs within the 8 weeks (56 days) of treatment with PDR001 in combination with dabrafenib and trametinib and (2) meets any of the predefined criteria in [Table 6-6](#). NCI CTCAE v4.03 (<http://ctep.cancer.gov>) will be used for grading of DLTs and adverse events in this protocol.

Table 6-6 Criteria for defining dose-limiting toxicities

TOXICITY	DLT CRITERIA (NCI CTCAE v4.03 will be used for grading)
Hematological	
 • Grade 4 anemia • Grade 4 neutropenia (for > 7 consecutive days) or Grade 4 febrile neutropenia • Grade 4 thrombocytopenia (of any duration). • Grade 3 thrombocytopenia with clinically significant bleeding regardless of duration or requirement of platelet transfusion
Hepato-biliary	
 • Grade 4 bilirubin elevation • For subjects with normal baseline AST and ALT values: 
 • AST or ALT > 8.0 × ULN • For subjects with normal baseline AST and ALT and normal baseline bilirubin value: 
 • AST or ALT > 3.0 × ULN combined with total bilirubin > 2.0 × ULN without evidence of cholestasis • For subjects with abnormal baseline AST or ALT or abnormal baseline bilirubin value: 
 • [AST or ALT > 2 × baseline AND > 3.0 × ULN] OR [AST or ALT > 8.0 × ULN], combined with [TBIL > 2 × baseline AND > 2.0 × ULN] without evidence of cholestasis
Gastrointestinal	
 • Nausea and vomiting ≥ Grade 3 for > 3 days despite optimal anti-emetic therapy. • ≥ Grade 3 diarrhea for > 5 days despite optimal antidiarrheal treatment (which could include steroids).
Pancreas	
 • Symptomatic serum amylase or lipase elevation, medical intervention required (Pancreatitis Grade 3 or higher)
Hypertension	
 • ≥ Grade 3 hypertension related to the study medication if it persists > 7 days despite optimal anti-hypertensive treatment • Grade 4 hypertension of any duration
Cardiac	
 • ≥ Grade 3 cardiac event that is symptomatic or requires medical intervention

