Pneumonitis	
 • Grade 2 pneumonitis if it persists > 7 days despite treatment with corticosteroids. • ≥ Grade 3 pneumonitis of any duration
Immune-related toxicities (except pneumonitis)	
 • Grade 3 immune-related toxicities that persist > 14 days with same severity despite treatment with corticosteroids. • Grade 4 immune related toxicities of any duration • ≥ Grade 3 infusion related reaction
Other Adverse Events	
 • Other clinically significant adverse events: 
 • ≥ Grade 3 adverse events that has not been previously identified for dabrafenib/trametinib and/or PDR001. • ≥ Grade 3 AEs that are known to occur with dabrafenib, trametinib and/or PDR001, but cannot be controlled using the recommended product-specific management guidelines or leads to 50% of planned exposure of study medications • Other clinically significant toxicities, including a single event or multiple occurrences of the same event that lead to a dosing delay of > 12 weeks should be considered to be DLTs by the Investigators and Novartis, even if not Grade 3 or higher.

TOXICITY	DLT CRITERIA (NCI CTCAE v4.03 will be used for grading)

Events which will NOT be considered as DLT for the purpose of this protocol:
 
• Clinically insignificant laboratory values \leq Grade 2. For laboratory values \geq Grade 3, the maximum allowable time limit for correction of electrolyte abnormalities to \leq Grade 1 is 72 hr.• Cutaneous squamous cell carcinoma (CuSCC), basal cell carcinoma, and new primary melanoma which are manageable with surgical excision alone	

The investigator must notify Novartis within less than 24 hours of any unexpected CTCAE v4.03 \geq Grade 3 AEs or laboratory abnormalities.

Dose modification during DLT observation period

If a subject experiences a DLT, during the DLT observation period, then treatment with dabrafenib, trametinib and PDR001 must be interrupted and the subject may be discontinued from the study depending on the severity of the DLT. However, following resolution of the DLT to CTCAE v4.03 Grade 1 or baseline value, the subject may continue to receive study treatment at a reduced dose level, if appropriate, at the discretion of the investigator.

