	
(Infliximab is contraindicated in subjects with sepsis or a perforation). Upon symptomatic relief initiate a prolonged steroid taper over 45 to 60 days.
 
 If symptoms worsen during steroid reduction, initiate a re-tapering of steroids starting at a higher dose followed by a more prolonged taper and administer infliximab. If symptoms persist despite the above treatment, a surgical consult should be obtained. 	
 Permanently discontinue dabrafenib and trametinib.
Grade 4: Life-threatening consequences; urgent intervention indicated	
 Same as Grade 3 	
 Permanently discontinue PDR001/placebo, dabrafenib and trametinib.

6.3.3.2 Mandatory dose modifications and recommended clinical management guidelines for abnormal liver enzyme test

Guidelines for dose modification and management of abnormal liver enzyme functions considered to be related to study treatment by the investigator are provided in [Table 6-10](#).

In addition to the instructions below, subjects with normal baseline transaminases and bilirubin who experience sudden elevations even within Grade 1, should be monitored more closely.

Table 6-10 Mandatory dose modifications and recommended clinical management guidelines for abnormal liver enzyme test

Abnormal liver enzyme tests/hepatitis		
Grade	Recommended adverse event management guidelines	Mandatory dose modification requirements
Grade 2: AST or ALT >3× ULN to ≤ 5× ULN and/or bilirubin > 1.5× ULN to ≤ 3× ULN	
 Monitor hepatic laboratory tests more frequently (every 2-3 days) until returned to baseline values 	
 Interrupt PDR001/placebo, dabrafenib and trametinib until ≤ Grade 1, and then reinstate PDR001/placebo, dabrafenib and trametinib at the same dose level.

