Grade 3 or 4: AST or ALT > 5× ULN and/or bilirubin > 3× ULN	
 Monitor hepatic laboratory tests more frequently (every 2-3 days) until return to baseline values. Consider appropriate consultation* with hepatologist and liver biopsy to establish etiology of hepatic injury, if necessary If after 2-3 days new liver assessment shows worsening of laboratory test consider to initiate treatment with high dose steroids (1 to 2 mg/kg/day prednisone or equivalents) 	
 Permanently discontinue PDR001/placebo only if causality is suspected to be related to PDR001/placebo ** If lab results show worsening, follow the management and dose modification (instructions below) 
1st occurrence
 
 Interrupt dabrafenib and trametinib until recovery to ≤ Grade 1 or baseline 
 Reduce dabrafenib and trametinib to the next lower dose level per Table 6-7. Re-escalation of the subject's

Abnormal liver enzyme tests/hepatitis

Grade	Recommended adverse event management guidelines	Mandatory dose modification requirements
	
 Add prophylactic antibiotics for opportunistic infections Start steroid taper as outlined in Section 6.3.4.1 if symptoms improve to Grade ≤ 1 If serum transaminase levels do not decrease 48 hours after initiation of systemic steroids, oral mycophenolate mofetil 500 mg every 12 hours may be given. Infliximab is not recommended due to its potential for hepatotoxicity 	
dose is recommended if criteria in Section 6.3.2 are met.
 
 If no recovery to \leq Grade 2 within 10 weeks, permanently discontinue dabrafenib and trametinib. 
2nd occurrence
 
 Interrupt dabrafenib and trametinib until \leq Grade 1. Reduce dabrafenib and trametinib to the next lower dose level per Table 6-7. Re-escalation of the subject's dose is recommended if criteria in Section 6.3.2 are met. 
3rd occurrence
 
 Permanently discontinue dabrafenib and trametinib

*Rule out viral hepatitis and other potential causes of liver injury

**For patients with liver metastasis who begin treatment with Grade 2 AST or ALT, if AST or ALT increase by $\geq 50\%$ relative to baseline and last for at least 1 week then the patient should be discontinued

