6.3.6.2 Follow up on potential drug-induced liver injury (DILI) cases

[figure not shown]
Subjects with transaminase increase combined with an elevation of total bilirubin (TBIL) may be indicative of potential DILI; these events should be considered as clinically important.

The threshold for potential DILI may depend on the subject's baseline AST/ALT and TBIL value; subjects meeting any of the following criteria will require further follow-up as outlined below:

- For subjects with normal ALT and AST and TBIL value at baseline: AST or ALT > 3.0 x ULN combined with TBIL > 2.0 x ULN
- For subjects with elevated AST or ALT or TBIL value at baseline: [AST or ALT > 2 x baseline AND > 3.0 x ULN] OR [AST or ALT > 8.0 x ULN], combined with [TBIL > 2 x baseline AND > 2.0 x ULN]

Medical review needs to ensure that liver test elevations are not caused by cholestasis, defined as ALP elevation > 2.0 x ULN with R value < 2 in subjects without bone metastasis, or elevation of ALP liver fraction in subjects with bone metastasis.

Note: (The R value is calculated by dividing the ALT by the ALP, using multiples of the ULN for both values. It denotes whether the relative pattern of ALT and/or ALP elevation is due to cholestatic ($R \leq 2$), hepatocellular ($R \geq 5$), or mixed ($R > 2$ and < 5) liver injury).

In the absence of cholestasis, these subjects should be immediately discontinued from study drug treatment, and repeat LFT testing as soon as possible, preferably within 48 hours from the awareness of the abnormal results. The evaluation should include laboratory tests, detailed history, physical assessment and the possibility of liver metastasis or new liver lesions, obstructions/compressions, etc.

1. Laboratory tests should include ALT, AST, albumin, creatine kinase, total bilirubin, direct and indirect bilirubin, GGT, prothrombin time (PT)/INR and alkaline phosphatase.
2. A detailed history, including relevant information, such as review of ethanol, concomitant medications, herbal remedies, supplement consumption, history of any pre-existing liver conditions or risk factors, should be collected.
3. Further testing for acute hepatitis A, B, C or E infection and liver imaging (e.g., biliary tract) may be warranted.
4. Additional testing for other hepatotropic viral infection (e.g., CMV, EBV, Adenovirus, HSV, HHV6, HIV), autoimmune hepatitis or liver biopsy may be considered as clinically indicated or after consultation with specialist/hepatologist.

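### Table 6-10 restarts all three drugs at the same dose in liver cases that Section 6.3.6.2 says to discontinue, and the text supplied does not say which rule governs

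*Protocol*

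**What the plan says.** Table 6-10 in Protocol Section 6.3.3.2 governs liver test abnormalities that the investigator considers related to study treatment. Its right-hand column is headed as mandatory.

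- **Grade 2 row:** AST or ALT above 3 and up to 5 x ULN, and/or bilirubin above 1.5 and up to 3 x ULN. The action is "Interrupt PDR001/placebo, dabrafenib and trametinib until ≤ Grade 1, and then reinstate PDR001/placebo, dabrafenib and trametinib at the same dose level".
- **Grade 3 or 4 row:** AST or ALT above 5 x ULN, and/or bilirubin above 3 x ULN. For the antibody: "Permanently discontinue PDR001/placebo only if causality is suspected to be related to PDR001/placebo". For the two targeted drugs, after interruption and recovery at the first and second occurrence: "Reduce dabrafenib and trametinib to the next lower dose level per Table 6-7". At the third occurrence both are stopped permanently.

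Section 6.3.6.2 sets criteria for potential drug-induced liver injury. With normal baseline the criterion is "AST or ALT > 3.0 x ULN combined with TBIL > 2.0 x ULN". The action is "In the absence of cholestasis, these subjects should be immediately discontinued from study drug treatment", with liver tests repeated as soon as possible and a work-up for other causes. No route back to treatment is given.

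The Glossary of terms defines study treatment discontinuation as "Point/time when patient permanently stops taking study treatment for any reason" and defines interruption separately, as a delay or withholding. The note under Table 6-10 refers to Section 6.3.6.2 for further information on following up potential liver injury cases and says nothing about which rule takes priority.

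**The concern.** Combined transaminase and bilirubin elevation without cholestasis is the pattern that Section 6.3.6.2 singles out as clinically important. Once confirmed with no other cause, it is reported as a serious adverse event. Table 6-10 has no exception for it. Because the table joins its ranges with and/or, the combined elevation is handled in the same way as an isolated rise in one test.

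Two investigators who both follow the protocol could therefore treat the same patient differently. One restarts all three drugs at full dose after recovery, and the other stops them for good. Section 2.6 lists hepatic abnormalities among the possible overlapping toxicities of the three drugs and cites the dose modification and stopping rules as patient safeguards, so the rechallenge rule should be unambiguous. What is at stake is patient safety. No estimate or test depends on it.

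**Working it through.** No sample size, power or error-rate figure is involved. The check is whether the two threshold rules cover the same patients.

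**Inputs** (normal baseline; A = AST or ALT, B = total bilirubin, both in multiples of ULN)

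- Liver injury criterion, Section 6.3.6.2: A > 3 and B > 2.
- Table 6-10, Grade 3 or 4 row: A > 5 and/or B > 3.
- Table 6-10, Grade 2 row: A in (3, 5] and/or B in (1.5, 3], and not Grade 3 or 4.

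**Overlap.** Take any case with A > 3 and B > 2.

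1. If A > 5 or B > 3, it is in the Grade 3 or 4 row.
2. Otherwise A is in (3, 5] and B is in (2, 3], so it is in the Grade 2 row.

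These two possibilities are exhaustive, so no normal-baseline case meeting Section 6.3.6.2 falls outside the table. A grid in steps of 0.1 x ULN (A from 0.5 to 20, B from 0.5 to 10) agrees:

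- Points meeting the criterion: 170 values of A (3.1 to 20.0) times 80 values of B (2.1 to 10.0) = 13,600.
- In the Grade 2 row: 20 values of A (3.1 to 5.0) times 10 values of B (2.1 to 3.0) = 200.
- In the Grade 3 or 4 row: 13,600 - 200 = 13,400.
- In neither: 0.

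These counts show coverage of the thresholds. They say nothing about how often patients have such values.

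**Actions side by side** (treatment-related, no cholestasis, first occurrence)

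| Case | Table 6-10 | Section 6.3.6.2 |
|---|---|---|
| A = 3.5, B = 2.5 (Grade 2 row) | Interrupt all three drugs, then restart all three at the same dose | Discontinue; no restart route |
| A = 6, B = 2.5 (Grade 3 or 4 row) | Interrupt dabrafenib and trametinib, then resume at a lower dose; stop PDR001/placebo permanently only if it is the suspected cause | Discontinue; no restart route |

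The overlap is not confined to normal baseline. ALT of 4.5 from a baseline of 2.0, with bilirubin of 2.5 from a baseline of 0.9, meets the abnormal-baseline criterion (4.5 > 2 x 2.0 = 4.0 and 4.5 > 3; 2.5 > 2 x 0.9 = 1.8 and 2.5 > 2). It falls in the Grade 2 row.

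**Extent of the conflict.** In the Grade 2 row the two rules agree on stopping at once and on early retesting, and differ on what follows recovery. In the Grade 3 or 4 row the difference concerns dabrafenib and trametinib at the first and second occurrence, and PDR001/placebo only when it is not the suspected cause.

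**The case against.** The strongest reply is that the rules work in sequence. Section 6.3.6.2 is the narrower rule, and the note under Table 6-10 points to it, so the specific section should govern the subset it names. Its instruction to stop, retest preferably within 48 hours and look for other causes also reads like a hold pending work-up, after which the table would apply by grade. The protocol often adds the word permanently when it means a final stop. Its use of discontinuation is also not strict: the Grade 4 row of Table 6-18 pairs permanent discontinuation of PDR001/placebo with an option to restart.

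This reading is possible, but the protocol does not state it. The note mentions follow-up only. The glossary separates discontinuation from interruption, and Table 6-10 uses the latter term for holds. Section 6.3.6.2 distinguishes confirmed, unexplained cases only for serious adverse event reporting and never to permit a restart. The wording also tilts the wrong way, since the table is mandatory while Section 6.3.6.2 says should.

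The objection does limit the scope. A reader might infer that Table 6-10 restarts all study drugs in every potential liver injury case. It does not: the Grade 3 or 4 row contains no instruction to restart PDR001/placebo.

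A reader might also count the Part 1 rule in Section 6.2.4 as a third conflicting outcome, because the same laboratory pattern is a dose-limiting toxicity there and treatment may then resume at a reduced dose. That rule is permissive and general to all such toxicities. The Amendment 6 rationale reports that all 9 Part 1 patients had completed the observation period, so it reaches no current patient.

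The remaining exposure is also short. Amendment 7 is dated 27 January 2023. Section 4.3 closes the study once every remaining subject has at least 5 years from randomization, and the last randomized patient's first treatment was on 11 July 2018, which points to about mid-2023.

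**Conclusion.** The conflict stands, limited to rechallenge. It is complete in the Grade 2 row for AST or ALT above 3 and up to 5 x ULN with bilirubin above 2 and up to 3 x ULN, and partial in the Grade 3 or 4 row. Followed literally, the mandatory column allows a potential drug-induced liver injury case to be restarted on all three drugs at full dose.

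The number affected is unknown. The Amendment 7 rationale gives 2 + 1 + 88 = 91 patients still on treatment. A reader might take that as the size, but it counts everyone still exposed and not those with the liver pattern. Placebo stopped after unblinding, so same-dose restart of all three drugs can apply only to patients still receiving PDR001, whose number is not given. Nothing in the documents supports an effect on the efficacy design or analysis.

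The conclusion assumes that the glossary meaning of discontinuation applies in Section 6.3.6.2. It also rests on the text at hand: the protocol as supplied ends within the Section 7.1 visit schedule, so a precedence rule later in the document cannot be excluded. The point is a patient-safety wording correction that should be made.

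**What to change.** 1. Add to both the Grade 2 row and the Grade 3 or 4 row of Table 6-10: *Cases meeting the Section 6.3.6.2 criteria without cholestasis follow Section 6.3.6.2 and are not restarted under this table, except where Section 6.3.6.2 allows it.*
2. State in Section 6.3.6.2 whether the stop is permanent for cases confirmed on repeat testing with no alternative cause.
3. State in Section 6.3.6.2 that any other case may resume under Table 6-10 only once an alternative cause is documented or the repeat test does not confirm the criteria.

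If the sponsor intends a hold pending work-up, items 2 and 3 are where to say so.

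The cost is one sentence in each of two table rows, one or two sentences in Section 6.3.6.2, and a letter to investigators. Sample size, endpoints and analysis do not change.

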Trial participants who have been exposed to someone infected by COVID-19 and/or who develop symptoms indicative of potential COVID-19 infection (see above) should contact the Investigator and discuss the next steps; these may include self-quarantine, or may require further testing/follow-up as appropriate. Administration of the study treatment may be delayed based on the risk benefit assessment until the trial participant completes the quarantine and remains asymptomatic and/or COVID-19 infection has been ruled out. Investigators are recommended to follow the local health authority guidelines for prevention against COVID-19.

[figure not shown]
[figure not shown]

Table 6-7 Dose modification steps for PDR001/placebo, dabrafenib and trametinib

Dose modification for PDR001 or placebo ^a				
	Starting dose level	Dose level - 1		
PDR001 or placebo	400 mg Q4W 400 mg Q8W (only if DL-1a is determined to be the dose regimen)	Not applicable		
Dose reduction for dabrafenib ^{a, b}				
	Starting dose level	Dose level - 1	Dose level - 2	Dose level - 3
Dabrafenib	150 mg BID (300 mg/day)	100 mg BID (200 mg/day)	75 mg BID (150 mg/day)	50 mg BID (100 mg/day)
Dose reduction for trametinib ^{a, b}				
	Starting dose level	Dose level - 1	Dose level - 2	Dose level - 3
Trametinib	2 mg QD	1.5 mg QD	1.0 mg QD	-
Q4W: once in every 4 weeks; BID: twice daily; QD: once daily				
^a . Dose modification should be based on the worst toxicity demonstrated at the last dose.				
^b . Dose reduction below 50 mg BID for dabrafenib and 1.0 mg QD for trametinib are not allowed.				

Table 6-8 Reference of AEs and toxicity management guidelines

Adverse Events	PDR001	dabrafenib	trametinib	Guideline
Diarrhea/colitis	X	X	X	Section 6.3.3.1 Table 6-9.
Abnormal liver enzyme test	X	X	X	Section 6.3.3.2 Table 6-10.
Skin rash	X	X	X	Section 6.3.3.3 Table 6-11.
Serious skin reaction	X	X	X	Section 6.3.3.4
Nephritis	X	X	X	Section 6.3.3.5 Table 6-12
Pneumonitis	X	X	X	Section 6.3.3.6 Table 6-13
Encephalitis	X	X	X	Section 6.3.3.7 Table 6-14
Endocrine events	X	X	X	Section 6.3.3.8 Table 6-15
Hand foot skin reaction	X	X	X	Section 6.3.3.9 Table 6-16
Neutropenia and thrombocytopenia	X	X	X	Section 6.3.3.10 Table 6-17
Adverse events including abnormal laboratory related AEs	X	X	X	Section 6.3.3.11 Table 6-18
Asymptomatic amylase and/or lipase elevation	X	X	X	Section 6.3.3.11 Table 6-18
Others	X	X	X	Section 6.3.3.12 Table 6-19
Infusion reaction and cytokine release syndrome	X			Section 6.3.4 Table 6-20

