6.3.1 General dose modification instructions for PDR001 or placebo

No dose reductions are allowed for PDR001. Dose interruption for PDR001/placebo includes delaying or withholding the treatment for any reason as well as an interruption of treatment during an infusion. Subjects with adverse events suspected to be related to PDR001 or placebo including those of potential immune-mediated etiology (irAE) (see definition in [Section 6.3](#)) must be permanently discontinued from PDR001 or placebo if (1) the AE doesn't recover to ≤ Grade 1 or baseline within 12 weeks and/or (2) the dose of steroids (for the management of irAE) remains > 10 mg/day prednisone or equivalent for >12 weeks.

The 12 week timeframe will begin from the time the irAE reaches a grade that leads to PDR001/placebo interruption.

Subjects who discontinue the study for a study related adverse event or an abnormal laboratory value must be followed as described in [Section 7](#).

6.3.2 General dose modification instructions for dabrafenib and trametinib:

[figure not shown]
If treatment related toxicities occur that are specific to combination treatment of dabrafenib and trametinib, then both treatments should be simultaneously dose reduced, interrupted or discontinued with the exceptions shown below:

Exception where dose modification is necessary for **only dabrafenib**:

- Uveitis ([Table 6-25](#))

Exception where dose modifications are necessary for **only trametinib**:

- Retinal vein occlusions (RVO) ([Table 6-25](#)) and retinal pigment epithelial detachment (RPED) ([Table 6-26](#))
- Left ventricular ejection fraction (LVEF) reduction ([Table 6-22](#))

If a subject’s dose of dabrafenib and trametinib has been reduced per the dose modification instructions, re-escalation of the subject’s dose is recommended provided the following criteria are met:

- a period of 4 weeks of treatment has passed since restarting dosing at the lower dose level and there is no recurrence of the AE
- the subject is deriving clinical benefit

For dabrafenib and/or trametinib related adverse events: if following an interruption of dabrafenib and trametinib, an AE doesn’t recover to ≤ Grade 1 or baseline within 4 weeks, dabrafenib and trametinib must be discontinued.

6.3.3 Dose modification and management guideline for adverse events common to PDR001, dabrafenib and trametinib

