Adverse events that have been reported with PDR001, dabrafenib or trametinib include, but are not limited to diarrhea/colitis, abnormal liver enzymes, skin rash, nephritis, pneumonitis, encephalitis, and endocrinopathies. It is possible that these and /or other adverse events may be exacerbated when PDR001, dabrafenib and trametinib are combined. Therefore, it is important to note that the management guidelines for the combination of PDR001, dabrafenib and trametinib may differ for a given AE from the management guidelines for each agent or combination treatment of dabrafenib and trametinib.

6.3.3.1 Mandatory dose modifications and recommended clinical management guidelines for diarrhea/colitis

Guidelines for dose modification and management for diarrhea and colitis considered to be related to study treatment by the investigator are provided in [Table 6-9](#).

Table 6-9 Mandatory dose modifications and recommended clinical management guidelines for diarrhea/colitis

CTCAE v4.03	Recommended adverse event management guidelines	Mandatory dose modification requirements
Grade 1 diarrhea (increase of <4 stools per day over baseline; mild increase in ostomy output compared to baseline) OR Grade 1 colitis (asymptomatic; clinical or diagnostic observations only; intervention not indicated) OR Grade 2 diarrhea (increase of 4 - 6 stools per day over baseline; moderate increase in ostomy output compared to baseline) OR	
 • Diet: stop all lactose containing products; eat small meals, BRAT diet (banana, rice, apples, toast) • Hydration: 8-10 large glasses of clear liquids per day (e.g., Gatorade or broth) • Loperamide: initially 4 mg, followed by 2 mg every four hours or after every unformed stool; maximum 16 mg/day. Continue until diarrhea free for 12 hours; • Diarrhea > 24hr: loperamide 2 mg every two hours; maximum 16 mg/day. Consider adding oral antibiotics. • Diarrhea > 48hr: loperamide 2 mg every two hours; maximum 16 mg/day. Consider other 	
 • Continue PDR001/placebo, dabrafenib and trametinib at the same dose level. • If diarrhea is Grade 2, despite loperamide at 2 mg every two hours for > 48hr: • Interrupt PDR001/placebo, dabrafenib and trametinib until ≤ Grade 1, and then reinstate PDR001, dabrafenib and trametinib at the same dose level.

CTCAE v4.03	Recommended adverse event management guidelines	Mandatory dose modification requirements

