6.3.4.1 Guidance for corticosteroids tapering for management of immune-related AEs

Reduce prednisone dose by 2.5 to 5.0 mg decrements every 3–7 days until physiologic dose (5 to 7.5 mg of prednisone per day) is reached. Consider to complete tapering over a period of at least 4 weeks. Slower tapering of corticosteroids therapy may be recommended if the adverse event is not showing improvement. Once corticosteroid tapering is achieved at a level of ≤ 10 mg of prednisone/day (or equivalent), PDR001 can be restarted as indicated in the dose modification tables.

6.3.5 Dose modification and management guideline for adverse events suspected to be related to dabrafenib and/or trametinib

Continue PRD001/placebo.

For adverse events of special interest reported **only for dabrafenib and/or trametinib**, general guidelines for dose modification in [Table 6-21](#) should be followed for dabrafenib and trametinib.

In general, if an AE resolves to Grade 1 or baseline at the reduced dose level, and no additional toxicities are seen after 4 weeks of study treatment at the reduced dose, the dose may be increased to the previous dose level.

A dose reduction below 50 mg BID for dabrafenib or below 1 mg QD for trametinib is not allowed. If a dose reduction below 50 mg BID for dabrafenib is required, dabrafenib will be permanently discontinued but these subjects will be allowed to continue trametinib. If a dose reduction below 1.0 mg QD for trametinib is required, then trametinib will be permanently discontinued, but these subjects will be allowed to continue dabrafenib.

[figure not shown]

Table 6-21 General guidelines for dose modification for adverse events suspected to be related to dabrafenib and/or trametinib treatment

Grade	Recommended adverse event management guidelines	Mandatory dose modification requirements
Grade 1 or Grade 2 tolerable	
 Monitor closely. Provide supportive care according to institutional standards. 	
 Continue dabrafenib and trametinib at the same dose level.

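### Table 6-10 makes the dabrafenib/trametinib hold for Grade 3 or 4 liver tests depend on laboratory worsening, while Grade 2 requires the hold outright

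*Protocol*

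**What the plan says.** Section 6.3.3.2 covers abnormal liver tests that the investigator considers related to study treatment. Table 6-8 assigns this event to "Section 6.3.3.2 Table 6-10", so that table governs.

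- **Grade 2 row, mandatory column:** "Interrupt PDR001/placebo, dabrafenib and trametinib until ≤ Grade 1, and then reinstate PDR001/placebo, dabrafenib and trametinib at the same dose level". No condition is attached.
- **Grade 3 or 4 row (AST or ALT above 5 x ULN and/or bilirubin above 3 x ULN), mandatory column:** PDR001/placebo is stopped permanently only if it is the suspected cause. The next line is "If lab results show worsening, follow the management and dose modification (instructions below" (the bracket closes there). After it come the 1st, 2nd and 3rd occurrence steps, the first being "Interrupt dabrafenib and trametinib until recovery to ≤ Grade 1 or baseline", followed by a reduction of one dose level.
- **Grade 3 or 4 row, management column:** "If after 2-3 days new liver assessment shows worsening of laboratory test consider to initiate treatment with high dose steroids". Here worsening means deterioration on a recheck, and what it triggers is steroids.

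**The concern.** The lead-in points to instructions below it, and the only instructions below it are the occurrence steps for dabrafenib and trametinib. As written, a Grade 3 or 4 elevation that is stable or improving on recheck triggers neither a hold nor a reduction of these two drugs. The more severe grade then carries the weaker mandatory action.

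Hepatic abnormality is one of the toxicities that Section 2.6 expects to overlap across the three drugs. In the pembrolizumab triplet study described in Section 2.1, 2 of 14 evaluable patients had Grade 3 or 4 transaminase elevations as dose-limiting toxicities. The event is therefore foreseeable.

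One site may follow the sentence and keep both drugs at full dose. Another may follow the row heading and stop both. The choice also decides whether the event counts toward the stepwise reductions and the discontinuation at the third occurrence.

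**Working it through.** The protocol gives no figure to reproduce here. The check sets the texts side by side.

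**1. Two patients under Table 6-10, read literally.** In both, bilirubin is normal, PDR001 is not suspected, and the liver-metastasis footnote does not apply.

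- ALT 4 x ULN (Grade 2): dabrafenib and trametinib held, 2 of 2.
- ALT 6 x ULN (Grade 3) at first detection, flat on recheck: held, 0 of 2.

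**2. Dosing during one recheck interval without the hold.** Doses are those of Table 6-4 and the 2-3 day interval is from the management column.

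- Dabrafenib: 2-3 days x 2 doses/day = 4-6 doses; x 150 mg = 600-900 mg.
- Trametinib: 2-3 days x 1 dose/day = 2-3 doses; x 2 mg = 4-6 mg.

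**3. Does other text supply the hold?**

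- Section 6.3.2 says of dabrafenib and trametinib "then both treatments should be simultaneously dose reduced, interrupted or discontinued". It states that they move together, not when.
- Table 6-21 is introduced for events of special interest reported "only for dabrafenib and/or trametinib". Table 6-8 lists liver tests under all three drugs.
- Section 6.3.3 warns that "the management guidelines for the combination of PDR001, dabrafenib and trametinib may differ for a given AE from the management guidelines for each agent", so single-agent rules cannot be assumed to carry over.
- The liver-injury rule in Section 6.3.6.2 stops treatment only when raised transaminases are combined with raised bilirubin.
- The dose-limiting-toxicity hold applies to the 8-week window of Part 1. Its transaminase-only threshold in Table 6-6 is above 8 x ULN, for patients with normal baseline values.
- The double-asterisk footnote to Table 6-10 covers only patients with liver metastasis who start with Grade 2 AST or ALT.

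None of these clearly reaches the patient at 6 x ULN.

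**4. Is the condition usual in this protocol?** Ten Section 6.3.3 tables have a Grade 3 row. Leaving out Table 6-10, 9 remain:

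| Table | Event | Drugs held at first Grade 3 event (of dabrafenib, trametinib) | Hold needs later worsening? |
|---|---|---|---|
| 6-9 | Diarrhea/colitis | both | no |
| 6-11 | Rash | both | no |
| 6-12 | Renal | both | no |
| 6-13 | Pneumonitis | trametinib only | no |
| 6-14 | Encephalitis | both | no |
| 6-16 | Hand-foot reaction | both | no |
| 6-17 | Neutropenia row | both | no |
| 6-18 | Other and laboratory AEs | both | no |
| 6-19 | Other AEs of special interest | both | no |

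Both drugs are held in 8 of 9, trametinib alone in 1 of 9, and a worsening condition appears in 0 of 9. In Table 6-17, Grade 3 thrombocytopenia without significant bleeding continues treatment; that exception is stated outright and does not depend on a recheck.

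**The case against.** - **Worsening could mean worse than baseline.** The dose cell names no comparator. Entry requires AST and ALT below 2.5 x ULN, or below 5 x ULN with liver metastasis, so any value above 5 x ULN is already worse than at entry. But on that reading the sentence has no function for transaminases, and the same row uses the word for a recheck after 2-3 days.
- **The literal reading defeats itself.** The sentence conditions the management as well, including the monitoring that would detect worsening. This shows that the sentence is badly placed. It does not create a hold.
- **Sister tables use similar wording only to move up a grade.** Tables 6-13 and 6-14 do this in lower-grade rows, as an addition to a hold of PDR001/placebo (and, for Grade 2 pneumonitis, trametinib) already required. In Table 6-10 the phrase sits inside the top grade.
- **Intent.** The Amendment 4 summary describes the first and second occurrence steps as guidance for Grade 3 or 4 increases, with no condition. That text is a change log, but it supports the view that an unconditional hold was meant. This point stands, and it argues for correcting the sentence.
- **Layout.** Bullets may have been lost in extraction. Even as a separate bullet, the sentence still conditions what follows it.
- **Tables 6-18 and 6-21 would hold both drugs.** The heading of Table 6-18 does not except liver tests, and the title of Section 6.3.5 is broader than its lead-in. Table 6-8 nevertheless sends liver tests to Table 6-10, so at best the texts conflict. It is true that no text tells a site to continue treatment.
- **Narrow reach.** A patient already held at Grade 2 stays held until Grade 1 or better. Randomization is complete, 91 patients (2 + 1 + 88) were on treatment at Amendment 7, and no endpoint or analysis is affected. All of this stands and limits the size of the point.

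**Conclusion.** The concern holds. As written, Table 6-10 requires both drugs to be held at 3-5 x ULN but ties the hold above 5 x ULN to further worsening, and no other text clearly closes the gap.

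It bites on events first detected at Grade 3 or 4 that are stable or improving on recheck, without the combined bilirubin rise that triggers the liver-injury rule, and outside the Part 1 and liver-metastasis provisions. The protocol does not say how many such events there were, and none is claimed. Investigators may also have stopped the drugs on clinical judgment.

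The conclusion rests on reading worsening as the same row's management column does. It should be fixed because it is a mandatory patient-safety rule for an expected overlapping toxicity. Confidence is medium, since the unconditional reading is probably what was intended.

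**What to change.** Delete the worsening sentence from the dose-modification column of the Grade 3 or 4 row and replace it with: *For every Grade 3 or 4 event, interrupt dabrafenib and trametinib at first detection and apply the 1st, 2nd and 3rd occurrence steps, whether or not laboratory results worsen.* Leave worsening after 2-3 days in the management column as the trigger for considering steroids. No change to the PDR001 rule is needed.

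The cost is one sentence in one table cell at the next amendment, plus a letter to sites. The downside is possibly a few more recorded dabrafenib and trametinib interruptions. The sponsor has revised this table before (Amendments 3 and 4), and Amendment 7 reworded Tables 6-13, 6-17 and 6-18, partly for clarity.
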